6.1.3 Study flow chart

Figure 2. Study design showing Radiesse treatment visits and X-ray schedule. Group A will be subjects with MHGS grade 4 hands at enrollment. Group B will be subjects with MHGS grade 2 or grade 3 hands at enrollment.

The figure does not show the initial screening visit or follow-up visits that will be scheduled 1-month after each optional retreatment received in the study.

6.1.4 Study timeline

Milestone	Relative to date of FDA Approval
Expected date of study initiation (First subject enrolled)	3 months
Expected monthly number of study sites with IRB approvals	N/A
Expected number of subjects enrolled per month	15
Expected date for completion of subject enrollment (Last subject, first visit)	5 months
Six Month Post-Approval Report to FDA	6 months
One Year Post-Approval Report to FDA	12 months
Eighteen Month Post-Approval Report to FDA	18 months
Two Year Post-Approval Report to FDA	24 months
Expected date for completion of study follow-up	29 months
Expected date for submission of final report	32 months

7 STUDY POPULATION

The study will enroll adults at least 22 years of age. There will be 2 study groups, with 10 subjects enrolled into each group. Group A subjects will be required to present with MHGS grade 4 hands at baseline. Grade 4 hands are defined as, in the dorsal hand: very severe loss of fatty tissue and marked visibility of veins and tendons. Group B subjects will be required to present with MHGS grade 2 or 3 hands at baseline. Grade 2 and 3 hands are defined as, in the dorsal hand: moderate to severe loss of fatty tissue and mild to moderate visibility of veins and tendons as determined by the investigator based on the MHGS. Group A subjects will provide radiographic assessment images of MHGS grade 4 hands, which might receive higher injection volumes than hands of Group B subjects. Every effort will be made to have all enrolled subjects complete the study. If subjects are withdrawn or lost to follow during the study, they will not be replaced.

7.1 Selection of study population

Presenting subjects will be screened to the selection criteria identified in sections 7.2 and 7.3 below. The investigational site will recruit and pre-screen candidates which could include use of patient databases, phone calls, email or postal mail distribution, and advertisements.

7.2 Inclusion criteria

Only subjects meeting all of the following inclusion criteria will be considered for study enrollment:

1. Has hands rating 2, 3, or 4 on the validated MHGS as determined by a live, masked evaluator.
 - Left and/or right hand with a rating of 4 of the validated MHGS will be assigned to Group A.
 - Left and right hands with a rating of 2 or 3 on the validated MHGS will be assigned to Group B.
3. Is at least 22 years of age.⁵
4. Has signed an ICF.
5. Understands and accepts the obligation not to receive any other procedures in the dorsum of the hands through the end of the study.

⁵ Pediatric populations or subpopulations generally do not suffer from the hand condition the device is intended to treat in the study protocol.

7.3 Exclusion criteria

Subjects having any of the following criteria, either at screening or at baseline, will not be included in the study:

1. Was a participant in the Radiesse hands pre-market clinical study (Merz #P110607).
2. Has been treated with fat injections or Radiesse in the hands, has hand deformities, or has received surgery in the dorsum of the hands.
3. Has received, within the past 6 months, or plans to receive dermal resurfacing procedures (e.g. chemical peel, dermabrasion, ablative laser resurfacing) or non-invasive skin-tightening (e.g. Thermage, Ulthera) in the dorsum of the hands during the study.
4. Has received in the past 2 weeks, or plans to receive during the study, prescription wrinkle therapies, topical steroids, skin irritating topical preparations, or pigmenting agents (self-tanning agents) in the dorsum of the hands during the study.
5. Has received, in the past 2 months, or plans to receive immunosuppressive medications or systemic steroids (intranasal / inhaled steroids acceptable) during the study.
6. Has an acute inflammatory process or infection, or history of chronic or recurrent infection or inflammation with the potential to interfere with the study results or increase the risk of AEs.
7. Has a known bleeding disorder or is receiving medication that will likely increase the risk of bleeding as the result of injection.
8. Has a known history of allergic / anaphylactic reactions, including hypersensitivity, to lidocaine or anesthetics of the amide type, or any of the device components.
9. Has a known history of hyper- or hypo-pigmentation, keloid formation, or hypertrophic scarring.
10. Is a female of child bearing potential⁶ and not using medically effective⁷ birth control or is pregnant or lactating.
11. Has any other medical condition with the potential to interfere with the study or increase the risk of adverse events, such as: autoimmune disease affecting the hand,

⁶ Childbearing potential is defined as NOT premenarche, permanently sterilized or postmenopausal (i.e., 12 months with no menses without an alternative medical cause).

⁷ Defined as a method that results in a low failure rate (i.e., less than 1% per year) when used consistently and correctly, such as implants, injectables, combined oral contraceptives, some IUDs, sexual abstinence, or vasectomized partner.

hand implants, Dupuytren's contracture, history of hand tumor, vascular malformations, Raynaud's disease, and patients at risk for tendon rupture.

12. Is enrolled or plans to enroll in an interfering study.
13. Is an employee or direct relative of an employee of the investigational site or of the study Sponsor.

7.4 Removal of subjects from treatment or assessment

7.4.1 Discontinuation of subjects

The subject may volunteer to discontinue or withdraw from the study at any time without any penalty or loss of benefits to which the subject is otherwise entitled. Date and discontinuation circumstances should be recorded.

Subjects must be discontinued from the study by the investigator at any time for any of the following reasons:

- Withdrawal of informed consent.
- Pregnancy.
- Any AE for which treatment continuation would constitute an unacceptably high risk for the subject.

Before discontinuation, every effort should be made to ensure that the subject returns for a final study visit. In the case of loss to follow-up subjects, every effort should be made to contact subjects lost to follow-up, and all such efforts should be documented in the subject file.

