6.1.1 Study visits

Subjects will be required to present for a total of up to 15 visits and 4 follow up phone calls. Of these visits, 7 to 10 are in-office investigational site visits and an additional 3 to 5 are X-ray visits at a licensed radiology center, and 1 to 4 are follow-up phone calls during their 24-month study participation.

If a subject only receives the initial treatment at enrollment, there will be a total of 7 in-office clinic visits, 3 x-ray visits and 1 follow-up phone call. For each of the 3 optional repeat treatments received, there will be an additional follow-up phone call (72 hours post injection). The fourth x-ray visit will only be required at Month 12 if no bones are visible

at the 6 month x-ray and the fifth x-ray visit will only be conducted if a subject receives four total treatments of Radiesse in this PAS study.

Following consent and enrollment at the site, subjects will have X-rays taken of their hands at the radiology imaging center. Each digital radiographic image taken in the study will be assessed by 2 independent blinded, licensed radiologists at the radiology core lab. After X-rays, all subjects will return to the study clinic to receive Radiesse treatment.

At 1-month, all subjects will have X-rays of their hands taken and will be assessed by the treating investigator for AEs.

At 6-months after enrollment, all subjects will have X-rays of their hands taken prior to receiving a repeat Radiesse treatment, if Radiesse retreatment is agreed upon by treating investigator and subject.

Subjects will have X-rays of their hands at 12-months only if bones of the hands were reported to be obscured by Radiesse by at least 1 radiologist on the 6-month X-rays, and will be assessed by the treating investigator for AEs. Subjects will receive repeat Radiesse treatments at 12- and 18-month follow-up visits if Radiesse retreatment is agreed upon by treating investigator and subject. If X-rays of the hands are required at 12 months, they will be taken prior to Radiesse retreatment.

Subjects will have X-rays at 24-months only if they receive 4 Radiesse treatments in the study; at enrollment, 6-, 12-, and 18-months after enrollment.

An additional 1-month follow-up visit and 72-hour follow-up phone call will be scheduled after each repeat treatment received at the 6-, 12-, and 18-month visits which would be at 7-, 13-, and 19-months, respectively.

6.1.2 *End of study*

[figure not shown]

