Month 6: 180 ± 10 days from enrollment, all subjects will return for a follow-up visit. Changes in concomitant medications will be recorded by the study staff. The subject's hands will be assessed on the MHGS by a live, masked evaluator. Subject self-assessment of aesthetic improvement will be performed using the GAIS. Subjects will complete the MHQ.

A physician will assess the subject's hands for AEs. A urine pregnancy test will be completed for female subjects of child bearing potential. A Radiesse retreatment will be performed on both hands if agreed upon by treating investigator and subject. A take-home 30-day diary will be given to the subject if a retreatment is received. Photographs of the hands will be taken only in the event of a serious or medically concerning AE.

72 hours after Month 6 retreatment: Only subjects receiving a retreatment at the Month 6 visit will be scheduled for a phone visit 72 hours after treatment to assess for adverse events. Subjects will be reminded to continue daily entries into their 30-day diary.

Month 7: $210 \text{ days} \pm 5$ days from enrollment, only subjects who received a retreatment at Month 6 will return for a follow-up visit. Changes in concomitant medications will be recorded by the study staff. The subject's hands will be assessed on the MHGS by a live, masked evaluator. Subject self-assessment of aesthetic improvement will be performed using the GAIS. Subjects will complete the MHQ.

A physician will assess the subject's hands for AEs. The take-home 30-day diary will be reviewed for completion and collected. Photographs of the hands will be taken only in the event of a serious or medically concerning AE.

Month 12 X-rays: 360 ± 10 days from enrollment, only subjects whose hand bones were not visible in the Month 6 X-rays will have X-rays taken of their hands at a designated, local, licensed imaging center. This visit must be completed prior to the Month 12 follow-up visit at the investigational site.

Month 12: 360 ± 10 days from enrollment, all subjects will return for a follow-up visit. Changes in concomitant medications will be recorded by the study staff. The subject's hands will be assessed on the MHGS by a live, masked evaluator. Subject self-assessment of aesthetic improvement will be performed using the GAIS. Subjects will complete the MHQ.

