10 SAFETY ASSESSMENTS

All AEs observed by study subjects, investigators or other study staff from informed consent through last study follow-up visit will be recorded. If a SAE or USADE occurs, study subjects may be requested to appear for unscheduled follow-up visits for AE assessment and hand photographs.

The following information, at minimum, must be recorded:

- AE description
- AE type (serious, expected, unexpected) – Refer to definitions below
- Start and Stop Dates
- Intensity (mild, moderate, severe) – Refer to definitions below
- Causal relationship (not related, related) – Refer to definitions below
- Treatment description, if any

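### Section 7.4.1 removes a subject from the study, not only from further Radiesse, when an AE makes more treatment too risky, so scheduled AE follow-up to Month 24 would be cut short

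*Protocol*

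**What the plan says.** Protocol 7.4.1 opens its list with "Subjects must be discontinued from the study by the investigator at any time for any of the following reasons". Three reasons follow: withdrawal of consent, pregnancy, and "Any AE for which treatment continuation would constitute an unacceptably high risk for the subject". The only follow-up attached to these exits is a best-effort contact: "Before discontinuation, every effort should be made to ensure that the subject returns for a final study visit". Section 7 adds that withdrawn subjects are not replaced.

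Retreatment is elective. For Months 6 and 12, and again for Month 18, Protocol 9.2 says "A Radiesse retreatment will be performed on both hands if agreed upon by treating investigator and subject", and 6.1.1 says the same of the later treatments: "Subjects will receive repeat Radiesse treatments at 12- and 18-month follow-up visits if Radiesse retreatment is agreed upon by treating investigator and subject". Section 6.1.1 also sets out what happens to someone who is never retreated: "If a subject only receives the initial treatment at enrollment, there will be a total of 7 in-office clinic visits, 3 x-ray visits" and one phone call.

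The AE collection window is in Protocol 10: "All AEs observed by study subjects, investigators or other study staff from informed consent through last study follow-up visit will be recorded". Start and stop dates are required for each event. Protocol 12.4.2 plans to summarize AE duration and recurrence. Section 12.3.3 plans rates of severe AEs attributed to the device or injection at Months 12, 18 and 24, and the incidence of all AEs across the study. The 1- and 6-month severe-AE rates are secondary (Protocol 5.2; SAP 6.2). SAP 4 analyses observed data on all enrolled subjects, and SAP 7.2 tabulates the reason for early withdrawal.

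**The concern.** The trigger and the consequence do not match. The trigger asks whether another injection would be too dangerous, and the natural response is to give no more injections. The rule instead ends the subject's participation. Someone who simply chooses not to be retreated is followed to Month 24, while someone harmed badly enough that retreatment is ruled out is not.

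The implant remains in the hand after exit. Once the last study visit has passed, Section 10 no longer calls for AEs to be recorded. Whether the triggering event resolves, whether it recurs, and whether a later event appears may therefore be missing. Because the AE itself causes the exit, the missing follow-up is tied to the outcome being summarized. In a post-approval safety study of 20 subjects without replacement, each such subject matters.

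**Working it through.** **Step 1. Does any clause separate stopping Radiesse from leaving the study?** The heading of 7.4 mentions treatment and assessment as alternatives, but the text of 7.4.1 provides only for exit from the study. The SAP has no rule on the matter. The provisions that could keep a subject under observation are these:

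| Provision | Covers | Requires scheduled follow-up after exit? |
|---|---|---|
| Final visit (7.4.1) | Any discontinuation | No: one best-effort contact, sought before exit |
| Unscheduled visits (9.2) | AEs of concern | No: at the investigator's discretion, not stated to run past exit |
| Unscheduled visits (10) | Any SAE or USADE | No: subjects may be asked to attend, not stated to run past exit |
| Prolonged end of study (6.1.2; SAP 2) | Unforeseen device-related SAE, or USADE | Not stated for a subject already discontinued |

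The gap is clearest for a non-serious AE that still reaches the 7.4.1 threshold.

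**Step 2. Follow-up lost per exit.** Inputs: 24 months of participation (6.1.1), and seven clinic visits without retreatment, namely screening, Week 1 and Months 1, 6, 12, 18 and 24 (6.1.1, 9.2). Months lost = 24 − exit month. Visits lost are those on the seven-visit schedule that fall after exit. The trigger presupposes that treatment could continue, so the latest exit that fits is Month 18, before the fourth injection.

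| Exit | Months lost | Share of 24 | Visits lost |
|---|---|---|---|
| Month 1 | 24 − 1 = 23 | 96% | 4 (Months 6, 12, 18, 24) |
| Month 7 | 24 − 7 = 17 | 71% | 3 (Months 12, 18, 24) |
| Month 13 | 24 − 13 = 11 | 46% | 2 (Months 18, 24) |
| Month 18, before injection | 24 − 18 = 6 | 25% | 1 (Month 24) |

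**Step 3. Share of the whole study.** Planned follow-up = 20 × 24 = 480 subject-months. The number of exits is not in the documents; 0 to 2 is an assumption.

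| Exit | One exit | Two exits |
|---|---|---|
| Month 1 | 23/480 = 4.8% | 46/480 = 9.6% |
| Month 7 | 17/480 = 3.5% | 34/480 = 7.1% |
| Month 13 | 11/480 = 2.3% | 22/480 = 4.6% |
| Month 18, before injection | 6/480 = 1.25% | 12/480 = 2.5% |

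With no exits the loss is zero.

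**Step 4. Films.** The Month 6 film is lost only if exit comes before Month 6, and the Month 1 film only if exit comes before Month 1. A Month 12 film is lost only where one was due: "Subjects will have X-rays of their hands at 12-months only if bones of the hands were reported to be obscured by Radiesse". The Month 24 film requires four treatments, so a subject whose Radiesse is stopped early would not have had one in any case.

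**Step 5. Effect on the primary result.** Suppose one or two subjects leave between Months 1 and 6 and no obscuration is seen in the rest. The exact 95% upper limit at Month 6 is 1 − 0.025^(1/n): 16.8% for 0/20, 17.6% for 0/19 and 18.5% for 0/18. The change is small.

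**The case against.** The strongest reply is that the schedule already solves the problem. Treatment here is one injection followed by elective ones, and nothing in the retreatment clause limits the investigator's reasons for declining. The investigator can decline and leave the subject on the seven-visit schedule. That works below the 7.4.1 threshold. At the threshold the wording is mandatory, so a site that follows the protocol has no such choice. How a site would act in practice is unknown, which is why the loss is conditional on the rule being applied.

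A second reply is that an AE grave enough to rule out another filler injection will often be serious. Section 10 would then allow unscheduled visits, and 6.1.2 might prolong the study. This has weight: it narrows the gap but does not close it, since neither provision requires scheduled visits after exit. A reader might infer that all AE information after exit is certain to be lost. The documents do not support that.

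A reader might also infer that every such exit weakens the objective on multiple retreatments (5.1). It does not. A subject removed before any retreatment could not inform that objective even with full follow-up, because under the fix that subject would receive no further Radiesse. Only subjects already retreated before exit count there.

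Finally, the number of exits is assumed, and the study is descriptive with no formal tests. Both points are right, and they keep the severity low.

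**Conclusion.** The point holds as a minor design flaw. As written, 7.4.1 ends study participation when the stated concern is only further treatment, and no other provision restores scheduled follow-up. The affected outputs are AE duration and recurrence, the 12-, 18- and 24-month severe-AE rates and whole-study AE incidence. For exits before Month 6, the 6-month severe-AE rate and the Month 6 film are affected too.

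The size is 6 to 23 months per affected subject for exits from Month 1 to Month 18. This rests on two assumptions: that sites apply the mandatory wording, and that an exit occurs at all. The triggering AE and any earlier films stay in the analysis. A reader might suspect that the rule distorts the obscuration result. Nothing in the documents shows that AEs at this threshold go with obscuration, so no bias in the primary result is shown.

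**What to change.** Amend 7.4.1 to distinguish stopping Radiesse from leaving the study. Suggested sense: *a subject who meets the AE criterion receives no further Radiesse but, unless consent is withdrawn, remains in the study on the no-retreatment schedule.* That means the remaining clinic and AE visits to Month 24, the Month 1 and Month 6 X-rays, and the Month 12 X-ray if bones were obscured at Month 6. Leave the medical threshold and the consent and pregnancy reasons as they are. Flag these subjects in the report.

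The cost is a few sentences in an amendment that needs IRB approval before use (3.1), with a consent-form revision if required (3.3). No subjects, readers or films are added beyond those planned. The burden is one to four already-planned clinic visits for exits from Month 1 onward, borne by subjects who have had an AE and who remain free to withdraw.

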7.4.2 Premature termination or suspension of the study or a study site

The study or the study site can be prematurely terminated or suspended by the Sponsor. If and when certain issues arise affecting the conduct of this Post Approval Study, the possibility of early study termination will be discussed with the FDA prior to termination. Reasons for termination of the study or a study site may include, but are not limited to, the following:

- Subject enrollment is unsatisfactory.
- The risks and benefits of continuing the study have been reassessed, and the risks outweigh any potential benefits.
- The incidence of AEs constitutes a potential health hazard to the subjects.

- New scientific data do not justify a continuation of the study.
- The investigator or study site exhibit serious and/or persistent non-adherence to the clinical study protocol and/or applicable regulatory requirements.
- The Sponsor decides to terminate the study at any time for any other reason.

Furthermore, the study may be prematurely ended if the regulatory authority or the IRB makes a recommendation to terminate or suspend approval for the study, the study site, or the investigator.

If the study is prematurely terminated or suspended for any reason, the investigator must inform the subjects and assure appropriate follow-up treatment. Within the timeframes noted in applicable regulations, the Sponsor will promptly inform the investigators, study sites, the IRB, and regulatory authorities of the termination or suspension of the study, as appropriate.

8 TREATMENTS

8.1 Investigational product(s)

8.1.1 *Description of investigational product(s)*

Radiesse injectable implant is an opaque, sterile, non-pyrogenic, semi-solid, cohesive implant. The principle component is synthetic calcium hydroxylapatite suspended in a gel carrier that consists primarily of water (sterile water for injection USP), glycerin (USP), sodium carboxymethylcellulose (USP). Radiesse injectable implant (1.5cc syringe unit) has a CaHA particle size range of 25-45 microns and should be injected with a 25 gauge Outer Diameter to 27 gauge Inner Diameter needle. The same size needle should be utilized throughout the trial for an individual subject.

8.1.2 *Disposition of investigational product(s)*

Radiesse has been FDA approved for injection into the face since 2006 (PMA P050037 and PMA P005052), and was approved for hand augmentation to correct volume loss in the dorsum of the hand in 2015 (PMA P050052/S049, see IFU **Appendix A**). This same Radiesse formulation will be used in this study for injection, as approved in the indication for hand augmentation to correct volume loss in the dorsum of the hand. Radiesse will be mixed with 2% lidocaine HCl prior to injection – an approved use of Radiesse.

8.2 Treatment administration

8.2.1 *Randomization Procedures*

The study is not a randomized trial, and there are no randomization procedures.

8.2.2 *Treatment method*

Prior to injection, Radiesse will be mixed with 0.26cc of 2% Lidocaine HCl. Volume injected as well as any observed AEs will be recorded. A maximum of 2 1.5cc Radiesse syringes will be injected per hand, per treatment visit. Treatment and retreatment visits will be scheduled per Table 2. There will be no touch-up treatments performed in the study. Subjects will be dispensed a 30-day take-home diary on which to record AEs that may occur before their next visit (**Appendix B**).

Step-by-step injection instructions are as indicated below from the IFU in **Appendix A**.

Technique for Mixing Radiesse injectable implant and 2% Lidocaine HCl

The following components are required for the percutaneous injection procedure and mixing Radiesse injectable implant with lidocaine:

[figure not shown]
- Radiesse injectable implant syringe(s) – 1.5cc
- Sterile 27 gauge, 0.5" regular-wall needle with luer lock connector
- 3.0cc sterile polypropylene luer lock syringe [REDACTED]
- 0.2cc of [REDACTED] 2% lidocaine HCl for injection, USP solution (not supplied by Merz North America, Inc.)
- Sterile female-to-female luer lock connector [REDACTED]

The Radiesse, sterile needles, 3.0cc sterile polypropylene mixing syringe [REDACTED], and the female-to-female luer lock connector [REDACTED] will be provided in a kit by Merz North America, Inc. for the study. The lidocaine will not be supplied by Merz.

Component Assembly and Mixing Instructions

1. Remove foil pouch from the carton containing the Radiesse injectable implant syringe. Open the foil pouch by tearing at the notches (marked 1 and 2), and remove the syringe from the foil pouch. *There is a small amount of moisture normally present inside the foil pouch for sterilization purposes; this is not an indication of a defective product.*
2. Assemble the components and perform the mixing using sterile technique (see **Figure 3**).

Figure 3. Radiesse mixing components. Left to right: female-to-female luer lock connector, Radiesse 1.5cc syringe, 3.0cc mixing syringe, sterile 27 gauge, 0.5" needle

3. Draw the 0.26cc lidocaine into a 3.0cc sterile polypropylene mixing syringe fitted with a sterile 27 gauge, 0.5" needle.
4. Tap the mixing syringe, containing 0.26cc lidocaine and depress its push rod to remove all excess air.
5. Remove the sterile 27 gauge, 0.5" needle.

6. Remove the luer syringe cap from the distal end of the Radiesse syringe and firmly connect the mixing syringe to the Radiesse syringe using the female-to-female luer lock connector (see **Figures 4 and 5**).

Figure 4. Removal of cap from Radiesse syringe

[figure not shown]
[figure not shown]

Figure 5. Connecting Radiesse syringe to the mixing syringe

7. Mix the lidocaine and Radiesse by alternately depressing the plungers, first on the mixing syringe and then on the Radiesse syringe for 10 mixing strokes (each mixing stroke is 1 complete compression of the mixing syringe plunger followed by 1 complete compression of the Radiesse syringe plunger). Plungers are compressed firmly and quickly, at about 2 compressions per second (**Figure 6**).

Figure 6. Mixing strokes.

8. After mixing, remove the mixing syringe and the female-to-female luer lock connector and discard.
9. Fit the syringe containing the lidocaine and Radiesse mixture with a 27 ID gauge injection needle by twisting the syringe of Radiesse onto the luer lock fitting of the needle. *Tighten the needle securely to the syringe.* If excess Radiesse is on the surface of the luer lock fittings, it will need to be wiped clean with sterile gauze.
10. Proceed to the “Injection Procedure” below.

Injection Procedure for Hand Augmentation

1. Prepare subject for percutaneous injection using standard methods. Have the subject wash both hands with soapy water producing friction for 5-10 minutes and then prepare hands with suitable antiseptic. The treatment injection site may be marked for planned injection sites. Jewelry should be removed prior to injection and until post-procedure swelling has resolved.
2. Using the syringe of Radiesse injectable implant that has been mixed with lidocaine using the procedure described in “Mixing Instructions” above, and fitted with the injection needle, slowly push the syringe plunger until Radiesse injectable implant extrudes from the end of the needle performing aspiration before bolus injection to avoid intravascular injection. If leakage is noted at the luer fitting, wipe it clean with sterile gauze. It may be necessary to tighten the needle, remove the needle and clean the surfaces of the luer fitting or, in extreme cases, replace both the syringe and the needle. A new injection needle may be used for each syringe, or the same injection needle may be connected to each new syringe.
3. Locate the initial site for injection. Subjects are to receive injections in the dorsum of the hands between the 1st and 5th metacarpals. Injection should initially occur between the 2nd and 4th metacarpals, taking care not to inject close to the metacarpophalangeal joints. If necessary to achieve optimal correction, injection is also allowed between the 1st and 2nd, and 4th and 5th metacarpals.
4. Skin tenting should be performed to separate the skin from vascular and tendinous structures by using the thumb and forefinger of the non-injecting hand to lift skin over the dorsal aspect of the hand being treated.
5. Advance the needle between the subcutaneous layer and superficial fascia with the syringe parallel to the dorsum of the hand. Carefully push the plunger of the Radiesse injectable implant syringe to start the injection and inject the Radiesse injectable implant material in small boluses, 0.2 – 0.5cc/bolus. No more than 0.5cc should be injected per bolus. The number of boluses will vary depending on the extent of treatment desired. No more than 3cc of Radiesse injectable implant (2 syringes) will be injected per hand, per treatment session.
6. If significant resistance is encountered when pushing the plunger, the injection needle may be moved slightly to allow easier placement of the material or it may be necessary to change the injection needle.
7. Immediately after injection, cover the injection site with a sterile 4x4 gauze and have the subject sit on this hand while the contralateral hand is being injected.

This warms the Radiesse injectable implant making it more malleable for later massaging.

8. Treat the contralateral hand in the same manner as described in steps 2 through 6 above.
9. Immediately after injection of the contralateral hand, cover the injection site with a sterile 4x4 gauze and have the subject sit on this hand.
10. While the contralateral hand is warming, remove the gauze from the hand that was initially injected, have the subject make a fist with this hand, and gently massage the dorsum of the hand until Radiesse has been evenly spread across the dorsum, remaining distal to the wrist crease and proximal to the metacarpophalangeal joints.
11. Use a 1:1 correction factor. No overcorrection is needed.

